The BU Investigators have recently designed, built, and tested a proprietary first-generation of such a fully integrated BP system, referred to as the iLet and the iLet infusion set. The iLet is a dual-chamber infusion system that currently incorporates the Dexcom G4 CGM technology, a custom user interface with touchscreen display, and all of the mathematical dosing algorithms that were tested in and validated using the iPhone-based BP in outpatient studies over the past 3 years. The iLet infusion set provides 2 independent subcutaneous (SC) fluid pathways from the iLet to the patient (1 for insulin and the other for glucagon). One tube connects to the prefilled insulin cartridge and the other tube connects to the fillable (single-use) glucagon cartridge.

In order to provide automatic BG regulation, the iLet and the iPhone-based BP have the ability to deliver both insulin and glucagon. However, currently available glucagon formulations have limited stability at room temperature, necessitating frequent changes to the glucagon infusion set. Therefore, the current trial is designed to test the glucagon analog ZP4207 in the iLet and the iPhone-based BP, as this peptide analog of human glucagon is provided in a liquid formulation stable at room temperature.

Clinical Trial Protocol
ZP4207-16051

Version number: 8.0
Amendment 7.0
Date: 06 January 2017

The current trial is a first feasibility trial designed to use the first-generation iLet and iLet infusion set and the iPhone-based BP to compare ZP4207 with marketed glucagon (Lilly). The trial is intended to demonstrate the safety and tolerability of ZP4207 in the iLet and the iPhone-based BP and the feasibility of achieving comparable autonomous glycemic control. It is not intended to comprehensively demonstrate the definitive efficacy of the BP in extended, continuous daily use, but rather to demonstrate its functionality and accuracy in a practical, albeit very controlled, clinical setting. The trial is expected to provide practical information that will benefit the design of a next-generation iLet and iLet infusion set and help pave the way for a more comprehensive outpatient home-use Phase 2 trial and ultimately a pivotal trial where comprehensive safety and efficacy through continuous full daily use of the iLet with ZP4207 will be documented.

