3 TRIAL DESCRIPTION

3.1 Summary of Trial Design

This trial is a single-center, open-label, 2-part, randomized cross-over trial. The trial will enroll adult patients with T1DM and will assess the safety and efficacy of the BP using either the iLet or the iPhone platform using the glucagon analog ZP4207 versus Lilly glucagon. In Part 1, up to 10 patients will participate in two 1-day treatment arms in random order (iPhone-based BP using ZP4207 and iPhone-based BP using Lilly glucagon) according to a pre-generated randomization scheme. In Part 2, up to 10 new patients will participate in two 1-day treatment arms in random order (iLet using ZP4207 and iLet using Lilly glucagon) according to a pre-generated randomization scheme. Patients can only participate in 1 part of the trial. An interim database lock may occur upon completion of Part 1 of the trial to analyze the iPhone-based BP data. The iLet and the iPhone-based BP will also administer insulin (insulin lispro, Lilly Humalog) using the same BG control algorithm for all 4 treatment arms. The trial will be conducted at a single center, the MGH Diabetes Center in Boston, MA.

The overall trial design schematic is displayed in [Figure 2](#).

[figure not shown]

Clinical Trial Protocol
ZP4207-16051

[figure not shown]
Version number: 8.0
Amendment 7.0
Date: 06 January 2017

Figure 2. Trial Design Schematic

Part 1:

Part 2:

Patients can only participate in 1 part of the trial.
ADA = anti-drug antibodies; BP = bionic pancreas.

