11 STATISTICS

For all analysis, the 2 treatment arms from Part 1 (iPhone-based BP) will be compared, and the 2 treatment arms from Part 2 (iLet) will be compared. The analysis of Part 1 will be completely separate from the analysis of Part 2.

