11.2.2 Analysis of Efficacy

The analysis of BP function endpoints and glycemic endpoints will be on an intention-to-treat basis. In cases where a treatment arm was not completed (and that arm was not repeated according to protocol criteria), available data from that arm will be used in the data analysis.

The Shapiro-Wilk test will be used to determine the normality of the residuals for each comparison. Summary tables that display descriptive statistics, including percentages, means or medians, and standard deviation and/or ranges, as appropriate, will be provided.

A paired t-test or the Wilcoxon signed rank test for comparison of means with normally or non-normally distributed residuals, respectively, will be used. In a secondary analysis, any period effect and any interaction between treatment and period will be looked for, although no such interaction is predicted for the efficacy outcome. Further details will be included in the SAP.

The number of patients and proportions of severe hypoglycemic events, symptomatic hypoglycemia, and carbohydrate interventions due to hypoglycemia with the event counts will be summarized descriptively, and the proportions will be analyzed by a Fisher's exact test if data allow.

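### Section 11.2.2 leaves period out of the main efficacy comparison and lets a normality check on about 10 differences pick the test; a period-adjusted estimate with a confidence interval would cost almost nothing

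*Protocol*

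**What the plan says.** Section 11.2.2 (repeated in the synopsis) fixes three things.

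- The treatment comparison: "A paired t-test or the Wilcoxon signed rank test for comparison of means with normally or non-normally distributed residuals, respectively, will be used".
- The rule that selects the test: "The Shapiro-Wilk test will be used to determine the normality of the residuals for each comparison".
- The place of period: "In a secondary analysis, any period effect and any interaction between treatment and period will be looked for, although no such interaction is predicted". No consequence of finding either is stated.

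It then adds "Further details will be included in the SAP".

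Section 3.1 gives the size ("In Part 1, up to 10 patients will participate in two 1-day treatment arms in random order", and the same for Part 2). Section 11 adds that "The analysis of Part 1 will be completely separate from the analysis of Part 2", so each test rests on about 10 differences, not 20. Section 5 randomises visit order in blocks of two. Section 11.1 defines the Full Analysis Set as all randomised patients. Section 1.1 gives as one aim to show "the feasibility of achieving comparable autonomous glycemic control".

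**The concern.** Randomising order in pairs builds sequence and period into the design, but the main test does not use them. Any systematic difference between Visit 3 and Visit 4 then enters the error term. Once dropout or exclusion leaves the two sequences unequal, it enters the estimate as well. A paired test also has no place for a patient with no data at one visit, which does not fit a Full Analysis Set of all randomised patients.

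A normality test on about 10 differences is a weak basis for choosing a method separately for each endpoint. The text also describes both candidates as comparing means, which the signed rank test does not do. At stake are the precision and interpretability of the glycemic and device-function comparisons. The primary safety assessment is not affected.

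**Working it through.** The protocol gives no power or sample-size figure (Section 11.2.4), so there is nothing to reproduce.

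**Inputs from the protocol.** Up to 10 patients per part, so 5 per sequence if all complete (Sections 3.1, 5, 11). Section 11.2.4 expects 20 to 24 randomised, which is 10 to 12 per part if split evenly.

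**Assumed, because the protocol does not state them.** Two-sided 0.05; true treatment difference δ = 1; period effect π from 0 to 1; within-patient correlation ρ from 0.3 to 0.7. Effects are in units of the SD of the within-patient treatment difference.

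**1. Where a period effect goes.** The expected difference is δ + π in one sequence and δ − π in the other. The mean over n1 and n2 patients is off by π × (n1 − n2)/(n1 + n2):

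- 5:5 gives 0
- 5:4 gives 1/9 = 0.11 π
- 6:4 gives 2/10 = 0.2 π

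At 5:5 the estimate is unbiased, but the expected variance of the differences becomes 1 + π² × 10/9. That is 1.28 at π = 0.5 and 2.11 at π = 1, so the standard error is inflated by about 1.13 and 1.45. The test becomes conservative.

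**2. Power and size, n = 10 (5:5), δ = 1.** Power in the first row is from the noncentral t; the rest is from 50,000 simulated trials per setting.

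| π | Power, paired t (9 df) | Power, period-adjusted (8 df) | Real size of paired t |
|---|---|---|---|
| 0 | 80.3% | 79.1% | 5% |
| 0.25 | 78.5% | 79.2% | 4.5% |
| 0.5 | 72% | 79% | 3.0% |
| 0.75 | 62% | 79% | 1.6% |
| 1.0 | 48% | 79% | 0.7% |

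The adjusted test stays at about 5% throughout. With 6:6, power is 82% against 88% at π = 0.5 and 62% against 88% at π = 1.

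**3. Price of adjusting when π = 0.** The 95% CI half-width goes from t(0.975, 9)/√10 = 0.715 to t(0.975, 8)/√10 = 0.729. The ratio is 1.02, or 2% wider.

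**4. The normality gate.** At n = 10, Shapiro-Wilk rejects in 19% of samples from t(3), 15% from Laplace and 44% from an exponential shape. For symmetric differences the two-stage procedure has type I error of 4.6% to 5.2%. With normal data its power is 80.6%, the same as the t-test alone. The gate is uninformative rather than damaging.

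Zero-heavy endpoints are a separate matter. With m non-zero differences the smallest exact two-sided signed rank p-value is 2/2^m: 0.0625 at m = 5 and 0.031 at m = 6. At least 6 non-zero differences are therefore needed. Earlier bionic pancreas arms (Section 1.3, Figure 1) spent 0.6% to 1.5% of time below 60 mg/dL, which is 2.9 to 7.2 minutes of a 480-minute visit. Zero differences are plausible, although the raised basal rate in this trial makes low readings more likely than in those arms.

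**5. The interaction look.** In a two-period, two-treatment design this contrast compares patient sums between sequences, so it cannot be separated from carry-over or a sequence difference. The SD of the sum is √((1 + ρ)/(1 − ρ)): 1.36 at ρ = 0.3 and 2.38 at ρ = 0.7. With 5 against 5, the noncentrality for a 1-SD carry-over is 1/(1.36 × √(2/5)) = 1.16 and 1/(2.38 × √(2/5)) = 0.66. Power is about 18% and 9%. A carry-over of that size would bias the treatment estimate by 0.5 SD.

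**6. What non-significance would mean.** With a half-width near 0.72 SD, a true difference of 0.5 SD is non-significant 71% of the time, and one of 0.75 SD 44% of the time.

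**The case against.** The power loss is conditional. The protocol gives no period effect, the unadjusted test is about one point better when there is none, and the 48% and 0.7% figures need a period effect of a full SD. The design also limits such effects: Section 7.4.1 restarts the algorithm from body weight at each visit, has patients arrive fasted, and keeps the meal and, where possible, the basal rate the same. This stands, and it limits the size of the point. It does not remove the possibility, because the trial is open-label and the same section lets the basal rate be lowered during a visit at the Investigator's discretion.

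A reader might infer more than the documents support:

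- *Period is ignored altogether.* It is not; Section 11.2.2 examines it in a secondary analysis.
- *The normality gate makes the choice of test arbitrary or inflates error.* The figures above show almost no cost for symmetric differences. With skewed differences the error rate rises (about 10% for the exponential shape), but by about the same amount for the t-test, the signed rank test and the two-stage rule, so the gate is not the cause.
- *The interaction look undermines the main result.* The main test does not depend on it, and drug carry-over is unlikely given the short half-life (Section 1.4) and a washout of at least 24 hours (Section 7.4).
- *A non-significant test will be reported as comparable control.* No section says so. Section 1.1 speaks of feasibility and disclaims definitive efficacy. That question stays open for want of an interval estimate, which the SAP may supply; a period term alone would not settle it.

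Keeping one-visit patients adds little information, and Section 11.2.2 already uses data from an incomplete arm. Only a patient with no data at all in one arm is lost.

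**Conclusion.** The point holds as a recommendation. The protocol itself, not only the unseen SAP, fixes an unadjusted test chosen by a weak normality check as the main treatment comparison, in a design whose randomisation supports a period-adjusted one. The loss is nil without a period effect, 7 points of power at 0.5 SD and 31 points at 1 SD. Bias appears only with unequal sequences, at 0.11 to 0.2 times the period effect. These figures rest on an assumed 1-SD treatment effect, 10 patients per part and two-sided 0.05. Efficacy is secondary here and the trial was not powered, so the consequence is modest; the case for change is that it costs so little.

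**What to change.** In Section 11.2.2 and the synopsis:

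- Make the main efficacy analysis, within each part, a linear mixed model with treatment and period as fixed effects and patient as random, with small-sample degrees of freedom. Report the ZP4207-minus-glucagon difference with its 95% CI.
- Remove the Shapiro-Wilk rule. For skewed or zero-heavy endpoints, such as time in the lowest and highest glucose ranges, name the method in advance: a rank-sum or permutation test on period differences between the two sequences.
- Stop describing the signed rank test as comparing means.
- Report the treatment-by-period contrast descriptively at most, and state that a non-significant difference is not evidence of comparability.

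The cost is wording plus one degree of freedom: a CI about 2% wider and about one point of power if there is truly no period effect.

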3.3 Number of Patients

Up to 40 adult patients with T1DM can be enrolled. The upper bound is based on the expectation that some patients will be excluded after the Screening Visit and the possibility that some patients may have to be discontinued before completion (due to, for instance, inter-current illness or patient withdrawal). It is expected that up to 10 patients will complete each part of the trial protocol.

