5 ASSIGNMENT TO TREATMENT GROUPS

This trial is an open-label, 2-part, randomized cross-over trial. Patients who have completed the Screening Visit and meet all of the inclusion and none of exclusion criteria will be enrolled into the trial. In Part 1, up to 10 patients will participate in two 1-day treatment arms in random order (iPhone-based BP using ZP4207 and iPhone-based BP using Lilly glucagon) according to a pre-generated randomization scheme. In Part 2, up to 10 new patients will participate in two 1-day treatment arms in random order (iLet using ZP4207 and iLet using Lilly glucagon)

Clinical Trial Protocol
ZP4207-16051

Version number: 8.0
Amendment 7.0
Date: 06 January 2017

according to a pre-generated randomization scheme. Up to 2 patients may participate in the trial per day. The order of the treatment visits will be randomized in blocks of 2 patients.

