 - The basal rate of the patient's own insulin infusion pump will be changed to be 2-fold higher than weighted mean of the basal rate during the trial period. This is intended to increase the usage of glucagon during the treatment visit. The basal insulin rate may be decreased during the treatment visit at the discretion of the Investigator. To the extent possible, the same basal rate should be used at Visit 3 and Visit 4.
 - The patients will continue to wear their own infusion pump infusing at the temporary basal rate throughout the visit until the start of the structured exercise period, in addition to the BP.
 - The staff will start the BP as close as possible to a minute divisible by 5 minutes (i.e., on a 5-minute mark). The starting time will be considered Hour 0.
 - Additional calibrations will be performed at any of the BG checks throughout the day if the CGM value does not meet the ISO standard (<15 mg/dL difference for BG values <75 mg/dL; <20% absolute difference for BG values >75 mg/dL) at the time of the BG measurement AND it is a good time to calibrate (the CGM trend arrow is flat and there has been no carbohydrate intake in the last 30 minutes or glucagon boluses in the last 15 minutes).
 - Blood samples will be taken from the IV at least hourly and processed for plasma ZP4207/glucagon. If BG is <150 mg/dL, more frequent samples for plasma ZP4207/glucagon may be drawn at the discretion of the Investigator. The actual time of sampling will be recorded in the eCRF.
 - Plasma glucose samples will be taken from the IV at least hourly in parallel with ZP4207/glucagon exposure sampling and measured using the YSI 2300 STAT Plus. If the YSI 2300 STAT Plus and/or IV fails, the Nova StatStrip Xpress will be used for glucose measurements. If BG is <150 mg/dL, then sampling will be every 30 minutes. If BG is <100 mg/dL, then sampling will be every 20 minutes. If BG is <80 mg/dL, then

Clinical Trial Protocol
ZP4207-16051

Version number: 8.0
Amendment 7.0
Date: 06 January 2017

sampling will be every 10 minutes. The actual time of sampling will be recorded in the eCRF.

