11.2.4 Sample Size Determination

No formal sample size calculations were made. It is expected that between 20 and 24 patients will be randomized in the trial. The sample size is based on a clinical rather than statistical

Clinical Trial Protocol
ZP4207-16051

Version number: 8.0
Amendment 7.0
Date: 06 January 2017

rationale. The sample size is considered adequate to address the primary trial objective of exploring the safety of ZP4207 when used in the BP and with reference to Lilly glucagon used in the BP.

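### The main efficacy comparison has no period term although visit order is randomized and Visit 4 can differ from Visit 3; a period-adjusted estimate would cost little

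*Protocol*

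**What the plan says.** On the treatment comparison for the BP function and glycemic endpoints, Protocol 11.2.2 states: "A paired t-test or the Wilcoxon signed rank test for comparison of means with normally or non-normally distributed residuals, respectively, will be used". Period comes next, outside that comparison: "In a secondary analysis, any period effect and any interaction between treatment and period will be looked for". The section adds that no interaction is predicted for efficacy and leaves further details to the SAP.

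On allocation, Section 5 states: "The order of the treatment visits will be randomized in blocks of 2 patients". On size, Section 3.3 states: "It is expected that up to 10 patients will complete each part of the trial protocol", and Section 11 states: "The analysis of Part 1 will be completely separate from the analysis of Part 2". Section 11.2.4 adds "No formal sample size calculations were made" and "It is expected that between 20 and 24 patients will be randomized in the trial".

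On how alike the two visits are, Section 7.4.1 doubles the basal rate of the patient's own pump and lets the Investigator lower it during the visit. It then says: "To the extent possible, the same basal rate should be used at Visit 3 and Visit 4". The same section requires the same meal at the same time at both visits and starts the control algorithm from body weight alone.

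**The concern.** The paired test pools the two visit orders as if Visit 3 and Visit 4 were interchangeable. If they are not, the period shift adds to the drug difference in one order and subtracts from it in the other. That spread is counted as random error, although the randomized order would remove it.

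The procedures leave room for a shift. The basal rate can only be lowered, at discretion, and is matched across visits only as far as possible. A reduction made partway through Visit 3 could therefore be in place for more of Visit 4. The lunch bolus is agreed with the Investigator, and the trial is open-label. Insulin level bears directly on the glycemic endpoints.

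Each comparison rests on about ten patients, so extra error is costly. Section 1.1 aims to show that comparable glycemic control is feasible. With an inflated error term, a non-significant difference could too easily be taken for comparability. If the orders also become unequal, part of the period shift is reported as a drug effect.

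**Working it through.** **Plan's own figure.** There is none to reproduce: the protocol gives no alpha, power, effect size or SD. The shift, the effect and a two-sided 5% level below are assumptions, and ranges are shown.

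**Model.** For patient i let d = outcome on ZP4207 minus outcome on Lilly glucagon, with d = τ + sπ + e. Here τ is the drug effect and π the Visit 4 minus Visit 3 shift. s = +1 if ZP4207 is given at Visit 4 and −1 if at Visit 3, and SD(e) = 1. All sizes are therefore in SDs of the within-patient difference. n1 and n2 are the numbers with s = +1 and s = −1.

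**Orders.** Blocks of 2 give 5:5 when 10 are randomized in a part. Unequal orders need a loss or exclusion: one loss gives 5:4. If 24 are randomized and split evenly between the parts, each has 6:6, and two losses from the same order give 6:4.

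**Paired test at 5:5.** The mean of d is unbiased, but its SD becomes √(1 + π²·10/9):
- π = 0.25: √1.069 = 1.03
- π = 0.5: √1.278 = 1.13
- π = 1.0: √2.111 = 1.45

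**Period-adjusted estimate.** Average the two order-specific means of d. The standard error is (pooled SD/2)·√(1/n1 + 1/n2), on n1 + n2 − 2 df. π cancels at any split.

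**Results at 5:5** (100,000 simulated trials per setting; power for τ = 1):

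| Shift π | Paired: type I error | Paired: power | Adjusted: type I error | Adjusted: power |
|---|---|---|---|---|
| 0 | 5.0% | 80% | 5.0% | 79% |
| 0.25 | 4.4% | 78% | 5.1% | 79% |
| 0.5 | 3.0% | 72% | 4.9% | 79% |
| 1.0 | 0.7% | 48% | 4.8% | 79% |

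The ratio of confidence interval half-widths, paired to adjusted, is the inflated SD times t(9 df)/t(8 df) = 2.262/2.306. That is 1.13 × 0.981 = 1.11 at π = 0.5 and 1.45 × 0.981 = 1.43 at π = 1.0 (using unrounded SDs). The signed rank test behaves the same way: power 78%, 70% and 45% at π = 0, 0.5 and 1.0 (4,000 trials per setting).

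**Bias of the paired estimate** is π(n1 − n2)/(n1 + n2):
- 5:5: 0
- 5:4: 1/9 = 0.11π, or 0.06 SD at π = 0.5
- 6:4: 2/10 = 0.20π, or 0.10 SD at π = 0.5
- 5:3: 2/8 = 0.25π, or 0.13 SD at π = 0.5

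The simulated bias matched these values, and the adjusted estimate had none.

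**Cost of adjusting when there is no period effect** (power for τ = 1, adjusted against paired): 79.3% against 80.4% at 5:5; 72.7% against 74.9% at 5:4; 63.0% against 68.0% at 5:3. At 5:5 the difference detectable with 80% power moves from 1.00 to 1.01 SD.

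**Smallest exact two-sided p-value at 5:3.** Rank-sum: 2/56 = 0.036. Signed rank with 8 pairs: 2/2⁸ = 2/256 = 0.008.

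**The case against.** A reader might infer that the plan's rules make Visit 4 likely to differ. The documents do not support that. Several rules push the other way: the basal rate is to be matched where possible, the meal and its time are fixed, and the algorithm starts from weight alone. Nothing says that the bolus or staff handling at Visit 4 follows experience at Visit 3, and no period effect is stated or predicted. What stands is that the visits can differ.

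A reader might also infer that period is ignored. It is not: a secondary analysis looks for it, with detail left to the SAP. The choice of an unadjusted main test is nevertheless made in 11.2.2 itself, so the point is not just SAP detail.

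A third inference is inflated false positives. That was not found: the paired t-test's type I error did not exceed 5% at any split from 5:5 to 6:3 or any shift up to 1.5 SD.

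The loss is also negligible for small shifts (78% against 79% power at 0.25 SD), and bias needs unequal losses. Adjusting is not free at unequal orders. There the paired test can even show more power than the adjusted one, as at 5:3 with π = 0.5 (69.5% against 62.9%), but only because the bias in that run lay in the direction of the effect. Finally, the primary endpoint is safety and no power was planned. These points limit the weight of the concern but do not remove it.

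**Conclusion.** The concern holds in limited form. The main comparison for the secondary BP function and glycemic endpoints omits a term that the randomization supports, in a design that permits a period shift. If a shift occurs, the harm at balanced orders is lost precision: trivial at 0.25 SD, moderate at 0.5 SD (72% against 79% power) and large at 1.0 SD (48% against 79%). Bias arises only with unequal orders and is a modest fraction of the shift, 0.11 after one loss from 5:5.

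The figures assume normal differences, a 1-SD drug effect, a two-sided 5% level and a period shift whose size the protocol does not inform.

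The treatment-by-period test does not fill the gap. In a two-period, two-order design it is aliased with carry-over and order, and it compares about 5 with 5 patients. A reader might conclude that it must be deleted, but 11.2.2 does not use it to choose the main analysis, so it can stay as exploratory.

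**What to change.** In 11.2.2, make the period-adjusted estimate the main comparison. Take each patient's Visit 3 minus Visit 4 difference and compare the two randomized orders with a two-sample t-test; half the difference in means is the drug effect. A model with treatment, period and patient is equivalent. For skewed endpoints use the rank-sum analogue with a Hodges-Lehmann estimate. Keep the unadjusted paired or signed rank test as a sensitivity analysis. State that the treatment-by-period test is exploratory and will not be used to choose or interpret the main analysis.

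The change is to wording and one model term, with no new patients or data. The statistical price is one degree of freedom at balanced orders, the somewhat larger power loss at unequal orders shown in the working, and a coarser exact p-value for the rank-sum version when few patients remain.

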8.2.2 Glycemic

All of following metrics will be generated from the Dexcom G4 Platinum CGM data during each treatment visit:

- Fraction of time spent within each of the following glucose ranges:
 - <50 mg/dL
 - <60 mg/dL
 - <70 mg/dL
 - 70-120 mg/dL
 - 70-140 mg/dL
 - 70-180 mg/dL
 - >180 mg/dL
 - >250 mg/dL
 - >300 mg/dL
- Number of severe hypoglycemic events (patients unable to self-treat, requiring the assistance of another person)
- Number of episodes of symptomatic hypoglycemia
- Number of carbohydrate interventions for hypoglycemia
- Total grams of carbohydrates taken for hypoglycemia
- Mean CGM glucose

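### Symptomatic lows and carbohydrate interventions are defined as counts per visit, but the test named for them is an unpaired any-versus-none comparison with under about 10% power for a halved mean count

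*Protocol*

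**What the plan says.** The current protocol (Version 8.0, Amendment 7.0) lists among the glycemic endpoints in section 8.2.2 "Number of episodes of symptomatic hypoglycemia" and "Number of carbohydrate interventions for hypoglycemia", both generated for each treatment visit. Total grams of carbohydrate taken for hypoglycemia is listed separately.

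Section 11.2.2 first gives a general rule without an endpoint list: "A paired t-test or the Wilcoxon signed rank test for comparison of means with normally or non-normally distributed residuals, respectively, will be used". It then gives severe hypoglycemia, symptomatic hypoglycemia and carbohydrate interventions a sentence of their own: patient numbers and proportions "with the event counts will be summarized descriptively, and the proportions will be analyzed by a Fisher's exact test if data allow". The synopsis repeats this.

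The design is paired: "In Part 1, up to 10 patients will participate in two 1-day treatment arms in random order", and Part 2 has the same structure. Section 11 adds: "The analysis of Part 1 will be completely separate from the analysis of Part 2". Section 7.4.1 doubles the basal rate of the patient's own pump until the exercise period and gives the reason: "This is intended to increase the usage of glucagon during the treatment visit". It also allows the investigator to lower that rate.

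**The concern.** The endpoint is a count, but the test sees only whether the count is zero. A patient with one rescue on one drug and four on the other contributes no difference. Repeat events within a visit are foreseen: the visit combines a fast, a raised basal rate and exercise, and sections 7.4.1 and 7.4.3 provide for repeat carbohydrate treatment at 15-minute intervals while glucose stays below 50 mg/dL.

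Fisher's exact test also treats the two arms as independent samples, although each patient supplies both and the sentence just before it names paired tests.

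Preventing lows is the purpose of the glucagon channel, and section 1.1 presents the trial as showing that comparable glycemic control with ZP4207 is feasible. A non-significant result from a test with almost no power could be misread as evidence of comparability.

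**Working it through.** **No figure to reproduce.** Section 11.2.4 makes no sample size calculation, and the protocol gives no event rate, effect size or power for these endpoints.

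**Inputs from the protocol.** Up to 10 patients per part, each giving both arms (section 3.1), and parts not pooled (section 11). Section 11.2.4 says: "It is expected that between 20 and 24 patients will be randomized in the trial". An even split of 24 would give 12 per part.

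**Assumptions.** Two-sided alpha 0.05. Events per visit are Poisson with mean m, with or without a gamma patient effect (shape 2) shared by both visits. One arm has half the mean of the other.

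**Step 1: from counts to any/none.** P(at least one event) = 1 − exp(−m). Means of 2 and 1 give 86% and 63%; 4 and 2 give 98% and 86%.

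**Step 2: how large a split Fisher needs.** If all 10 patients have an event in one arm and 5 of 10 in the other, the five patients without an event all fall in one arm: p = 2 × C(10,5)/C(20,5) = 2 × 252/15,504 = 0.033. With 6 of 10 it is 2 × C(10,4)/C(20,4) = 2 × 210/4,845 = 0.087. So 10 of 10 against 5 or fewer is needed.

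**Step 3: power with 10 patients.** Fisher without a patient effect is exact: the sum, over all x and y, of Bin(x; 10, p1) × Bin(y; 10, p2) where Fisher's p ≤ 0.05. The other entries are simulated (2,000 runs each). The count test is the exact paired signed-rank test. Each cell shows without / with the patient effect.

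| Mean events per visit | Fisher, any/none | Signed-rank, counts |
|---|---|---|
| 0.5 vs 0.25 | 4% / 2% | 3% / 2% |
| 1 vs 0.5 | 7.5% / 3% | 11% / 8% |
| 2 vs 1 | 8% / 3% | 30% / 24% |
| 3 vs 1.5 | 3% / 2% | 45% / 38% |
| 4 vs 2 | 0.5% / 1% | 59% / 50% |

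The highest Fisher value for any halving examined is 9% (75% vs 50% of patients with an event). With 12 patients it is 14%. Repeat runs over the last three rows gave 22–56% for the count test, so differences of a few points should not be relied on.

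**Step 4: pairing alone does not help.** An exact McNemar test on the same any/none cut has about 6% power or less in these halving cases.

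**Step 5: clustering within a visit.** Repeat rescues in one unresolved low are not independent. With a visit-level gamma effect (shape 1 / shape 0.5), power is:

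| Mean events per visit | Fisher, any/none | Count test |
|---|---|---|
| 2 vs 1 | 4% / 3% | 12% / 8% |
| 3 vs 1.5 | 4% / 2% | 15% / 10% |
| 4 vs 2 | 2.5% / 3% | 17% / 10% |

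Repeat runs under within-visit clustering gave about 11–16% for the count test.

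**The case against.** Three stronger readings are tempting, and the documents support none of them.

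- **That most patients will have an event in both arms.** The protocol does not say so. The stated aim of the raised basal rate is more glucagon use, not a given frequency of lows, and the investigator may lower the rate. Carbohydrate is permitted below 60 mg/dL and required only below 50 mg/dL (section 7.4.3). Under the Poisson model without a patient effect, 54% of patients have an event in both arms at means of 2 vs 1, but only 25% at 1 vs 0.5. Low power comes first from having 10 patients; a ceiling would make it worse.
- **That this is the only inferential comparison of rescue.** Total grams of carbohydrate is outside the Fisher sentence and plausibly falls under the paired t-test or Wilcoxon rule. With 15 g per treatment, one rescue against four is 15 g against 60 g, and that difference would enter a paired test. The time-below-threshold endpoints are plausibly paired too.
- **That testing counts always gains a great deal.** It gains nothing at 0.5 vs 0.25, about 4–5 points at 1 vs 0.5, and far less under within-visit clustering than under Poisson.

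It can also be said that the general paired-test sentence might cover the counts and that an unseen SAP may settle this. The natural reading is against it, because the specific sentence that follows assigns the counts to description. Finally, these are secondary endpoints in a feasibility trial with no power claim, the counts will be reported, and the Fisher test is conditional on the data. That limits the severity but does not remove the mismatch.

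**Conclusion.** The point stands as a minor one. Two endpoints defined as counts are cut to any-versus-none for testing, and the test named ignores the pairing. For a halved mean count its power is under about 10% with 10 patients per part, and it approaches zero if lows turn out to be common.

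A paired test on the counts is clearly better under the Poisson assumptions when the arm with fewer events averages about one or more per visit. It is modestly better if events cluster, and no better when events are rare. All these figures rest on assumed rates and distributions. The loss is clearest for symptomatic episodes, which have no companion measure like total grams. Even after the change, power remains limited by the number of patients, so a null result would not show comparability.

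**What to change.** In section 11.2.2 and the synopsis:

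- For symptomatic episodes and carbohydrate interventions, compare the within-patient difference in counts (ZP4207 minus Lilly glucagon), separately in each part. Use an exact Wilcoxon signed-rank or paired permutation test, chosen in advance, and report a confidence interval.
- Keep the any/none proportions as description and drop Fisher's test.
- Leave severe hypoglycemia as description.
- State that a non-significant difference will not be interpreted as comparability.

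The cost is wording in 11.2.2, the synopsis and the SAP. The counts are already to be summarized, and the signed-rank test is already named in 11.2.2, so no new data are needed. The one drawback is that results are expressed as events per visit rather than as a percentage of patients.
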